9.3.1.4 Duration of Mechanical Ventilation up to Day 30

Duration of mechanical ventilation is defined as the cumulative periods (>1 hour) from start of IMP until Day 30, on mechanical ventilation. Mechanical ventilation during - and up to three hours after - surgery / procedure is exempt from this rule.

For patients withdrawn or dying while still on mechanical ventilation, the duration will be based on the data available up until the time of withdrawal or death.

Duration of mechanical ventilation will be analyzed separately for survivors, non-survivors (within the first 30 days) and overall using a zero inflated negative binomial model with time from onset of shock to start of treatment, and norepinephrine/noradrenaline requirement at baseline (μ g/kg/min) as covariates, and treatment and need for ventilation as factors. As duration of ventilation is derived with two decimal points (with values in the range of 0.00, 0.01, ..., 90.00), duration of ventilation

Page 32 of 80

will be transformed (for model stability) to integer values (with values in the range of 0, 1, ..., 9000) by multiplying with 100. Treatment estimates will be back transformed.

In case the model assumptions for duration of ventilation does not hold, the permutation test specified in Section 9.3.1.3 will be used including an analysis of the expected proportion of patients with 0 duration, and estimates of the duration for those with a positive duration.

9.3.1.5 Daily Overall and Individual Organ (Cardiovascular, Respiratory, Renal, Hepatic, Coagulation) Scores using the Modified Sequential Organ Failure Assessment (SOFA) Scores Until ICU Discharge

Last observation carried forward (LOCF) will be used for missing SOFA scores on Days 2-7. No LOCF for Day 1 (as previous value is baseline). Patients dying will be imputed with a worst possible outcome, i.e. a value of 4 for each individual SOFA score.

Daily overall (modified) and individual SOFA scores will be compared between treatment arms up until Day 7 using a repeated measures ANCOVA model with baseline SOFA score as covariate, treatment, time and treatment by time interaction as factors, baseline SOFA score by time interaction, and patient as the experimental unit. The estimated treatment difference (to placebo) with a 95% confidence interval will be presented.

Furthermore, daily overall and individual SOFA scores will be tabulated by treatment arm (including pooled active treatment arms).

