Incidence of RRT will be analysed by a logistic regression model with time from onset of shock to start of treatment, baseline creatinine and norepinephrine/noradrenaline requirement at baseline (µg/kg/min) as covariates, and treatment and need for ventilation as factors. The 95% confidence interval for the difference in proportions between treatment groups will be constructed using the delta method (see Appendix 4 for details). Patients already on RRT for chronic renal failure at time of inclusion will be excluded from the analysis of incidence of RRT.

Non-inferiority will be claimed if the upper limit of the two-sided 95% CI of the adjusted difference in proportions is less than 20% of the estimated incidence of RRT in the placebo group. Superiority can be claimed (5) if the upper limit is less than 0.

I.e., let $\widehat{p_S}$ and $\widehat{p_P}$ be the estimated incidences of RRT in the combined selepressin groups and the placebo group respectively. Non-inferiority will then be claimed if

$$\widehat{p_S} - \widehat{p_P} + 1.96 * \sqrt{var(\widehat{p_S} - \widehat{p_P})} < 0.2 * \widehat{p_P}$$

and superiority will be claimed if

$$\widehat{p_S} - \widehat{p_P} + 1.96 * \sqrt{var(\widehat{p_S} - \widehat{p_P})} < 0$$

A forest plot including the non-inferiority tests for all analyses will be presented.

Furthermore, incidence of RRT will be tabulated by treatment arm (including pooled active treatment arms).

A subgroup analysis will be performed on patients without acute RRT at baseline.

9.3.1.9 Duration of RRT up to Day 90 (excluding patients on RRT for chronic renal failure at time of randomisation)

Duration of RRT is defined as the cumulative periods with RRT (continuous renal replacement therapy, intermittent hemodialysis or peritoneal dialysis) and will be analyzed excluding patients on RRT for chronic renal failure at time of randomisation.

For patients withdrawn or dying while still on RRT, the duration will be based on the data available up until the time of withdrawal or death.

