Duration of RRT will be analyzed as for duration of ventilation (also by transforming to integers) in Section 9.3.1.4 with time from onset of shock to start of treatment, baseline creatinine and norepinephrine/noradrenaline requirement at baseline (μ g/kg/min) as covariates, and treatment and need for ventilation as factors. The supportive competing risk and Kaplan-Meier graphs described in Section 9.3.1.4 will not be performed as it makes no sense since RRT durations are short and repetitive. It is more meaningful to just look at 90 day mortality and withdrawal rates to take eventual skewed mortality and withdrawal rates into account.

Page 35 of 80

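### Duration of RRT runs to Day 90 but takes over a survivor split made at Day 30, so its survivor analysis is not free of truncation by death

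*SAP*

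**What the plan says.** Section 9.3.1.9 covers RRT time up to Day 90 and excludes patients on RRT for chronic renal failure at randomisation. The model is not written out there: "Duration of RRT will be analyzed as for duration of ventilation (also by transforming to integers) in Section 9.3.1.4". The section restates only the integer transformation, the covariates and the factors. For patients "dying while still on RRT, the duration will be based on the data available" up to that moment, and the same holds for withdrawal.

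Section 9.3.1.4, to which it refers, has a shorter window: "Duration of mechanical ventilation is defined as the cumulative periods (>1 hour) from start of IMP until Day 30, on mechanical ventilation". Its analysis is "analyzed separately for survivors, non-survivors (within the first 30 days) and overall using a zero inflated negative binomial model". No other survivor definition reaches the RRT endpoint.

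Section 9.3.1.9 also drops the supportive competing-risk and Kaplan-Meier graphs and gives a replacement: "It is more meaningful to just look at 90 day mortality", together with withdrawal rates.

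Section 9.3.1.4 describes ventilation duration, an endpoint that stops at Day 30, as a variable "with values in the range of 0.00, 0.01, ..., 90.00".

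**The concern.** A separate survivor analysis of a duration endpoint is useful because nobody in it has had the duration ended by death. That works only if survival is judged over the same window as the duration. Here the window is 90 days and survival is judged at 30, so the last 60 days are unprotected. A patient who is alive at Day 30 and dies later while still on RRT enters the survivor model with a value stopped by death. Neither section describes a censoring indicator or an exposure offset that would mark it as incomplete.

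At stake is what the survivor and non-survivor estimates for this endpoint mean. A reader would take the survivor result to be RRT time in people who lived through the observation window, and as written it is not that. There is also a risk of inconsistent programming, since one programmer may carry the Day 30 flag across and another may assume Day 90.

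**Working it through.** The SAP states no figure that depends on this point, so there is none to reproduce. The check compares the sections and then gives an illustration of scale.

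**Step 1: window against split, by endpoint.**

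| Endpoint (SAP section) | Window | Survivor status judged at |
|---|---|---|
| Duration of septic shock (9.3.1.3) | Day 30 | Day 30 |
| Duration of ventilation (9.3.1.4) | Day 30 | Day 30 |
| EQ-5D index and VAS (9.3.3.1) | Day 180 | Day 180 |
| QALY (9.3.3.1) | Day 30; Day 180 | Day 30; Day 180 |
| Duration of RRT (9.3.1.9) | Day 90 | Day 30, by reference to 9.3.1.4 |

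RRT duration is the only row where the two do not match. Section 9.3.1.3 also shows what the split is meant to do. It places truncation by death in the non-survivor analysis and leaves only withdrawal as a cause of truncation among survivors. The RRT analysis as written does not have that property.

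**Step 2: who is affected.** Under the literal text:
- Death by Day 30: non-survivor, as intended.
- Death on Days 31-90, on RRT at death: survivor, with the duration cut at death.
- Death on Days 31-90, off RRT at death: survivor. Recorded RRT time is not cut, although any later RRT the patient would have needed is lost.
- Alive at Day 90: survivor, as intended.

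**Step 3: scale of the misclassification (illustration).** Inputs:
- N = 1800 evaluable patients (section 3.2).
- Placebo mortality of 20-25% (section 9.3.2.3), taken here as Day-30 mortality m in all patients. This is an assumption.
- L, the share of all patients who die on Days 31-90. The SAP does not give it, so 2%, 5% and 8% are assumed.

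Share of Day-30 survivors who die by Day 90 = N × L / [N × (1 − m)].

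| L | Late deaths, 1800 × L | m = 20%: of 1440 | m = 25%: of 1350 |
|---|---|---|---|
| 2% | 36 | 2.5% | 2.7% |
| 5% | 90 | 6.25% | 6.7% |
| 8% | 144 | 10.0% | 10.7% |

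These percentages count all late deaths. Those with truncated RRT are a subset whose size the SAP does not allow one to estimate. The SAP also reports that the trial stopped for futility, so actual counts would be lower than those based on 1800.

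**Step 4: direction.** Take a patient on RRT without interruption from the start of IMP who dies on Day 35. The recorded value is 35 days, and 90 − 35 = 55 days of the window are unobserved. Against complete follow-up the value is short. Within the survivor group it may be long, because section 9.3.1.9 itself calls RRT episodes short and repetitive and the model allows for excess zeros. Including this patient raises the survivor mean whenever the mean of the others is below 35 days. The sign of the effect on the group mean, and so on the treatment difference, is therefore not fixed by the text.

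**The case against.** The strongest reply is that section 9.3.1.9 never says that late deaths count as survivors. It borrows a method, and the only mortality horizon it names itself is 90 days. The misplaced 90.00 in the ventilation section, and the reference to graphs in 9.3.1.4 that are in fact described in 9.3.1.3, suggest text moved between endpoints. A Day 90 split may well have been intended. That is plausible, but the SAP does not say it, and the only split the cross-reference supplies is at Day 30.

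A second reply is that the plan already handles differential mortality. It directs the reader to 90-day mortality and withdrawal rates, Day 90 mortality is a key secondary endpoint with its own model, and an overall analysis is planned that does not use the split. This stands in part. Those displays help a reader interpret the result, but they do not change who enters the survivor model. The overall analysis is itself shortened by death.

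A reader might go further and infer that an arm with more late deaths will show shorter RRT among survivors, or that a late death typically costs some 55 of 90 days. The documents support neither. The direction is open for the reason shown in the working. The 55 days apply only to uninterrupted RRT, whereas the endpoint sums periods on RRT and includes intermittent haemodialysis. Nor does the SAP say that late deaths are commoner in patients on RRT at Day 30.

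**Conclusion.** The point holds as a mismatch of horizons. Followed literally, section 9.3.1.9 analyses patients who die on Days 31-90 as survivors, and those on RRT at death contribute durations cut at death and treated as complete. The survivor analysis is therefore not free of truncation by death over its own window.

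The effect on the treatment comparison cannot be given a size or a sign from the SAP. Under the assumed late mortality of 2-8%, between 2.5% and 10.7% of Day-30 survivors would be misclassified, and a smaller, unknown share would lose RRT time. The consequence is limited: the overall RRT analysis does not depend on the split, and the endpoint is a non-key secondary outside the Hochberg procedure in section 9.3, so primary and key secondary inference is untouched. The change should still be made, because it is cheap and removes a real ambiguity in programming.

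The 0.00-90.00 range for ventilation is a separate editorial slip. It changes no derived value and adds no weight to the RRT point.

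**What to change.** In section 9.3.1.9, add one sentence stating that, for duration of RRT, survivors and non-survivors are defined by vital status at Day 90. In section 9.3.1.4, correct the ventilation range to 0.00-30.00, or 0-3000 after multiplication by 100.

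The cost is two sentences in the SAP and one survivor flag in the derivation. No new data are needed, because all-cause mortality at Day 90 is already a key secondary endpoint.

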9.3.2 Morbidity/Mortality

9.3.2.1 Intensive Care Unit (ICU)-free Days up to Day 30

ICU -free Days up to Day 30 will be defined and analyzed in a similar manner as the primary endpoint, with the van Elteren test stratified by need for ventilation (Yes/No), time from onset of shock to start of treatment (< or \ge 6 hours), and norepinephrine/noradrenaline requirement at baseline (< or \ge 30 µg/min) and baseline creatinine (< or \ge 150 µmol/L).

A sensitivity analysis will be performed where the definition of time spent in the ICU will include first admission to emergency department, as some patients will be enrolled and have first IMP treatment in the emergency department.

9.3.2.2 ICU Length of Stay up to Day 30

ICU length of stay is defined as the cumulative periods spent in ICU from start of IMP to 30 days after.

For patients withdrawn or dying while still in ICU up to Day 30, the duration will be based on the data available up until the time of withdrawal or death.

ICU length of stay will be analyzed between treatment groups using the permutation test specified in Section 9.3.1.3 stratified by the combination of time from onset of shock to start of treatment (< or \ge 6 hours), baseline creatinine (< or \ge 150 μ mol/L), norepinephrine/noradrenaline requirement at baseline (< or \ge 30 μ g/min) and need for ventilation (Yes/No).

A sensitivity analysis will be performed where the definition of time spent in the ICU will include first admission to emergency department, as some patients will be enrolled and have first IMP treatment in the emergency department.

9.3.2.3 All-cause Mortality (Defined as the Fraction of Patients That Have Died, Regardless of Cause, by the end of Day 30, Day 90, and Day 180)

Mortality will be analysed by a logistic regression model with the individual SOFA scores and age as covariates and treatment arm as factor. The 95% confidence interval for the difference in proportions between treatment groups will be constructed using the delta method as for incidence of RRT (section 9.3.1.8). There will be no imputations for mortality.

Non-inferiority will be claimed if the upper limit of the two-sided 95% CI of the adjusted difference in proportions is less than 30% of the estimated incidence of mortality in the placebo group. Superiority can be claimed (5) if the upper limit is less than 0.

I.e., let $\widehat{p_S}$ and $\widehat{p_P}$ be the estimated incidences of mortality in the combined selepressin groups and the placebo group respectively. Non-inferiority will then be claimed if

Page 36 of 80

$$\widehat{p_S} - \widehat{p_P} + 1.96 * \sqrt{var(\widehat{p_S} - \widehat{p_P})} < 0.3 * \widehat{p_P}$$

and superiority will be claimed if

$$\widehat{p_S} - \widehat{p_P} + 1.96 * \sqrt{var(\widehat{p_S} - \widehat{p_P})} < 0$$

Assuming observed mortality rates of 20-25% in the placebo group, a non-inferiority limit of 30% corresponds to a maximum observed mortality rate of 2-3% in the combined selepressin groups in order for selepressin to be non-inferior to placebo. A forest plot including the non-inferiority tests for all analyses will be presented.

Furthermore, mortality will be tabulated by treatment arm (including pooled active treatment arms), and the time to death presented graphically by a Kaplan-Meier plot.

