9.3.1 Organ Dysfunction

9.3.1.1 Vasopressor-free Days up to Day 30

Vasopressor-free Days up to Day 30 will be defined and analyzed in a similar manner as the primary endpoint, with the van Elteren test stratified by need for ventilation (Yes/No), time from onset of shock to start of treatment (< or \ge 6 hours), and norepinephrine/noradrenaline requirement at baseline (< or \ge 30 µg/min).

9.3.1.2 Mechanical Ventilator-free Days up to Day 30

Ventilator -free Days up to Day 30 will be defined and analyzed in a similar manner as the primary endpoint, with the van Elteren test stratified by need for ventilation (Yes/No), time from onset of shock to start of treatment (< or \ge 6 hours), and norepinephrine/noradrenaline requirement at baseline (< or \ge 30 µg/min).

9.3.1.3 Duration of Septic Shock up to Day 30

Duration of septic shock is defined as the cumulative periods (>1 hour) from start of IMP until Day 30, on IMP or vasopressors. Vasopressor use due to anaesthesia / procedure-induced hypotension during - and up to three hours after - surgery / procedure (including bedside) is exempt from this rule

For patients withdrawn (in the survivors analysis) or dying (in the non-survivors analysis) while still in septic shock, the duration will be based on the data available up until the time of withdrawal or death.

Duration of septic shock will be analyzed separately for survivors, non-survivors (within the first 30 days) and overall, comparing treatment arms by a negative binomial model with time from onset of shock to start of treatment and norepinephrine/noradrenaline requirement at baseline (µg/kg/min) as covariates, and treatment and need for ventilation (Yes/No) as factors. The estimated treatment difference (to placebo) with a 95% confidence interval will be presented. As duration of septic shock is derived with two decimal points (with values in the range of 0.00, 0.01, ..., 30.00), duration of septic shock MAY be transformed (for model stability) to integer values (with values in the range of 0, 1, ..., 3000) by multiplying with 100. Treatment estimates will be back transformed

Date: 20 Nov 2017 E-Statistical Analysis Plan-17877; Ver.9.0 Supersedes: Ver. 8.0 Page 31 of 80

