Some patients will get out of shock prior to Day 30 (and stay alive until Day 30), some will get out of shock and die later on (prior to Day 30), others will die or be withdrawn while still in shock (prior to Day 30), and the remaining few will not get out of shock prior to Day 30. This means that if mortality and withdrawal rates vary between treatment arms, the results of the analysis for the overall population will be influenced by the skewed mortality and withdrawal rates. Hence, for the overall population, the distribution of duration of shock (time to out of shock), will be presented graphically as competing risks between 'time to out of shock', 'withdrawn while in shock' and 'dying while in shock'. Further, Kaplan-Meier (sub)-graphs on 'time to death' and 'time to withdrawal' will be presented for those getting out of shock (for which some will die or be withdrawn later on, prior to Day 30). This is done in order to elucidate any skewness in mortality and withdrawal rates, influencing the results of the analysis.

Furthermore, duration of septic shock will be tabulated by treatment arm (including pooled active treatment arms).

In case the model assumptions does not hold, covariates will be dichotomised (in same manner as they have been dichotomised for other endpoint analyses) and duration of septic shock will be analysed using a stratified permutation test (Monte Carlo estimate of p-value). Treatment effects (and treatment difference) will be the raw (unadjusted/non-stratified) means. The confidence intervals for the individual treatment arms will be derived by bootstrapping 5000 samples (within treatment group) with same number of observations (within treatment group), and taking the 2.5 and 97.5% percentiles from the distribution of the 5000 means from the bootstrapped samples. The confidence interval for the treatment difference will be derived via significance testing (based on the stratified permutation test), i.e. the confidence interval will be constructed by including the 95% confidence region for all those values for which the significance test of the hypothesis that the true value is the given value is not rejected at a 5% significance level (e.g. if we test is treatment difference=1 and p-value >0.05 then we include 1 in the confidence interval, and so on). The seed for both the Monte Carlo derived p-value and the bootstrapped confidence intervals will (appropriately) be seed=133.

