9.4 Other Endpoints/Assessments

9.4.1 Hospital-free Days up to Day 90

Hospital stay is defined (from the eCRF) as "Other acute care hospital" or "Still in trial hospital"

Hospital-free Days up to Day 90 will be defined and analyzed in a similar manner as the primary endpoint, with the van Elteren test stratified by need for ventilation (Yes/No), time from onset of shock to start of treatment (< or \ge 6 hours), and norepinephrine/noradrenaline requirement at baseline (< or \ge 30 µg/min) and baseline creatinine (< or \ge 150 µmol/L).

9.4.2 Hospital Length of Stay up to Day 90

Hospital length of stay is defined as the cumulative periods spent in hospital ("Other acute care hospital" or "Still in trial hospital") from start of IMP to 90 days after.

For patients withdrawn or dying while still in hospital up to Day 90, the duration will be based on the data available up until the time of withdrawal or death.

Page 39 of 80

Hospital length of stay will be analyzed between treatment groups using the permutation test specified in Section 9.3.1.3 stratified by the combination of time from onset of shock to start of treatment (< or \ge 6 hours), baseline creatinine (< or \ge 150 μ mol/L), norepinephrine/noradrenaline requirement at baseline (< or \ge 30 μ g/min) and need for ventilation (Yes/No).

9.4.3 Patient Residence at Day 30, Day 60, Day 90, and Day 180

Patient location at Day 30, 60, 90 and 180 will be summarized by treatment arm (including pooled active treatment arms). Baseline is the timing prior to acute admission.

Shift tables will be presented at each time point to assess whether patients have returned to their location at enrollment. There will be no imputations of missing values.

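### ICU and hospital length of stay stop at death and are compared over all patients, without the survivor analyses and competing-risk display that the SAP requires for septic shock duration

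*SAP*

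**What the plan says.** SAP 9.3.2.2 defines ICU stay as cumulative time in ICU from start of IMP to 30 days. It then says: "For patients withdrawn or dying while still in ICU up to Day 30, the duration will be based on the data available" up to that event. Section 9.4.2 does the same for hospital stay to Day 90: "For patients withdrawn or dying while still in hospital up to Day 90, the duration will be based on the data available" until then.

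Each endpoint has one between-group comparison. For ICU stay: "ICU length of stay will be analyzed between treatment groups using the permutation test specified in Section 9.3.1.3". For hospital stay: "Hospital length of stay will be analyzed between treatment groups using the permutation test specified in Section 9.3.1.3". Both sections supply their own strata. Under that test, "Treatment effects (and treatment difference) will be the raw (unadjusted/non-stratified) means". Section 9.1 applies all efficacy analyses to the full analysis set. The only sensitivity analysis for ICU stay concerns emergency-department time.

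For septic shock duration, 9.3.1.3 also counts time only up to death or withdrawal, but goes further. "Duration of septic shock will be analyzed separately for survivors, non-survivors (within the first 30 days) and overall". It warns that, if mortality and withdrawal differ between arms, "the results of the analysis for the overall population will be influenced by the skewed mortality and withdrawal rates". For that reason the overall distribution "will be presented graphically as competing risks between 'time to out of shock', 'withdrawn while in shock' and 'dying while in shock", with Kaplan-Meier sub-graphs for those who leave shock.

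**The concern.** Stay ends either by discharge alive, which is good, or by death, which is not. An all-patient mean treats a day saved by either route alike. A patient who dies in ICU on Day 2 contributes 2 days, fewer than one discharged alive on Day 6. If those who die tend to have the shorter stays, an arm with more deaths gets a shorter mean stay and an arm that saves lives gets a longer one, even when treatment changes nothing else.

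The SAP recognises this mechanism for septic shock duration and gives safeguards against it. Ventilation duration (9.3.1.4) is also analysed by survival status. For RRT duration (9.3.1.9) the graphs are dropped with a stated reason, and the reader is pointed to 90-day mortality and withdrawal. The stay sections have neither the safeguards nor a reason for omitting them.

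At stake is the reading of a non-key secondary endpoint (ICU stay, 2.2.3) and an additional endpoint (hospital stay, 2.2.5). Section 9.3 says the pooled comparison determines success for the secondary efficacy endpoints, so the ICU result is not labelled as mere resource use.

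**Working it through.** **1. Text comparison**

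| | Shock duration (9.3.1.3) | ICU stay (9.3.2.2) | Hospital stay (9.4.2) |
|---|---|---|---|
| Time cut at death or withdrawal | yes | yes | yes |
| Overall comparison | yes | yes | yes |
| Survivors and non-survivors separately | yes | no | no |
| Competing-risk display | yes | no | no |
| Warning about differing mortality | yes | no | no |

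The cross-reference in both stay sections is to the permutation test only.

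**2. The plan's own figures.** The SAP states no mean or SD for stay, so no stay figure can be reproduced. The mortality input can be checked. Appendix 8 assumes 25% placebo mortality and 24 P&VFDs in survivors, so the overall mean is 0.75 × 24 = 18, as stated there. With 1.5 points lower mortality and 1.5 more days, 0.765 × 25.5 − 18 = 1.51, which agrees with the 1.5 P&VFDs in 3.2.

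**3. Size of the shift.** Let p be mortality, and let m_S and m_D be the mean stays of survivors and of patients who die, the same in both arms. Then mean stay = (1 − p)·m_S + p·m_D, and

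shift (active − placebo) = −(excess mortality) × (m_S − m_D).

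The variance within an arm is (1 − p)·SD_S² + p·SD_D² + p(1 − p)(m_S − m_D)². With n = 1000 vs 800, SE = √(V_active/1000 + V_placebo/800). The chance of a significantly shorter stay is Φ(−1.96 − shift/SE), a normal approximation to the permutation test.

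Assumed, not from the SAP: all stay means and SDs, the 1000:800 split of the planned 1800, and the use of 25% mortality for the Day 90 endpoint as well.

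Example, ICU 10 d (SD 8) vs 6 d (SD 6), 30% vs 25% mortality: shift = −0.05 × 4 = −0.20. V_placebo = 0.75·64 + 0.25·36 + 0.1875·16 = 60.0. V_active = 0.70·64 + 0.30·36 + 0.21·16 = 58.96. SE = √(0.05896 + 0.0750) = 0.37. Φ(−1.96 + 0.55) = 7.9%.

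| Assumed stay, survivors vs those who die (SD) | 2 points: shift, chance | 5 points: shift, chance |
|---|---|---|
| ICU 10 (8) vs 6 (6) | −0.08 d, 4.1% | −0.20 d, 7.9% |
| ICU 10 (8) vs 4 (4) | −0.12 d, 5.2% | −0.30 d, 12.9% |
| Hospital 25 (20) vs 9 (9) | −0.32 d, 5.4% | −0.80 d, 14.1% |
| Hospital 30 (22) vs 8 (8) | −0.44 d, 6.3% | −1.10 d, 18.8% |
| ICU 10 (8) vs 10 (8) | 0, 2.5% | 0, 2.5% |
| ICU 10 (8) vs 12 (9) | +0.04 d, 2.0% | +0.10 d, 1.3% |

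With no excess mortality every row gives 2.5%. The last two rows show that both the existence and the sign of the bias depend on the gap in stay.

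**4. Cross-check by simulation.** 4000 trials with 900 per arm; the same latent lognormal ICU stay in both arms (median 8 days, log-SD 0.9, capped at 30); death at a uniform point of that stay; z-test. The mean shift was −0.10 days at 2 points and −0.27 at 5 points. A significantly shorter stay occurred in 4.6% and 11.6% of trials, against 2.9% with no excess. ICU-free days moved against the arm with more deaths, by −0.37 and −0.96 days.

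**The case against.** The strongest case against is that the plan already holds death-penalised counterparts of equal or higher rank. ICU-free days to Day 30 is a key secondary endpoint under the Hochberg procedure, and hospital-free days to Day 90 is also planned. Both are defined like the primary endpoint, so death scores zero. Mortality is analysed separately with a Kaplan-Meier plot. A misleading stay result would therefore appear beside results that contradict it. This stands as mitigation, but those analyses do not change the stay estimate, its confidence interval or its p-value, and the SAP does not tie them to the stay result.

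The large figures also need 5 points of excess mortality. Section 11 stops the trial if the predictive probability of observing more than 2% higher mortality in the active arms exceeds 90%, which makes a large excess less likely to persist to full enrolment. Section 1 records that the trial ended for futility, so the full 1800 need not apply. This stands too: at 2 points the effect is small.

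Three stronger readings are tempting and are not supported:

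- A reader might infer that every death is scored as a short stay, or that the scale is simply reversed. The SAP counts actual days to death, so a death in ICU on Day 25 is a long stay.
- A reader might infer that a label claim is exposed. Neither stay endpoint is in the Hochberg family.
- A reader might infer that the overall test must give way to the cumulative incidence of live discharge. Section 9.3.1.3 keeps its overall test and adds to it. Replacement would change the estimand, and because stay is cumulative it would leave the handling of readmissions open.

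**Conclusion.** The point holds as an inconsistency with a moderate consequence. Sections 9.3.2.2 and 9.4.2 leave an all-patient comparison unprotected against a distortion that 9.3.1.3 names and guards against.

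If patients who die stay less long than survivors, the ICU shift under the stated assumptions is about 0.1 day at 2 points of excess mortality and 0.2-0.3 day at 5 points. The chance of a significantly shorter ICU stay rises from 2.5% to 4-5% and 8-13%. For hospital stay the shift is 0.3-0.4 and 0.8-1.1 days, with chances of 5-6% and 14-19%. Fewer deaths on active treatment would lengthen the mean stay in the same way. The direction and size rest on assumed stays that the SAP does not supply. The primary analysis and the key secondary endpoints are unaffected.

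**What to change.** Keep the overall permutation test in both sections, and add:

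1. Analyses of stay by survival status, to Day 30 for ICU stay and to Day 90 for hospital stay.
2. A competing-risk display of discharge alive, death and withdrawal, stating which discharge counts when a patient is readmitted.
3. A statement that the overall stay result is not read as efficacy on its own, but together with ICU-free days, hospital-free days and mortality.
4. A statement that the survivor-only comparison is supportive, because it conditions on an outcome after randomisation. If treatment keeps sicker patients alive, survivor stay can itself be biased.

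The cost is SAP wording and a few more outputs from data that the stay and mortality endpoints already use. The overall length-of-stay p-value becomes less prominent.
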